- 1. First, two videos will be created to counsel patients who have decided to undergo a MUS procedure. One video, the physician-centered video, will be developed with well-described literature involving the risks, benefits, and alternatives to MUS. Physicians from the urogynecology division will be videotaped explaining these risks. The second video will be the patient-centered video. We will meet with the patient mentors who were a mentor in the Preliminary Study of Peer Support Groups and Pelvic Floor Disorders. We will create a script with the patient mentors that will include the risks, benefits, and alternatives in lay terms as well as topics that have previously been identified by focus groups as important patient-centered aspects of counseling. This will include aspects of quality of life factors such as catheterization and when patients can return back to work. Once we have created the script with the mentors who agree to be filmed; the mentors will be videotaped explaining these topics. All participants involved in the creation of the video will sign an informed consent prior to the development of the video. The participants will include the physicians counseling on the video and women acting as mentors on the video.
- 2. Once the videos are complete, we will perform a randomized clinical trial clinical trial to determine if a patient-centered versus a physician-centered video will increase preparedness and satisfaction. The target population is female subjects with stress urinary incontinence who are planning to have a MUS procedure. All subjects will be given written study consents during their clinic visit when they are scheduled for their MUS. After enrollment, subject's data collected include *Patient Demographics*: Age; self-reported race and ethnicity; body mass index (BMI); vaginal parity, education level, socio-economic status. Also, *Medical/Surgical History*: Medical comorbidities; prior POP surgeries or incontinence procedures, prior hysterectomy. They will also perform a health literacy assessment utilizing the validated REALM-SF questionnaire. They will also complete the PGI-I and STAI: Y6 questionnaire at the baseline clinic visit.

Page 10 of 23

Version 5 Date: 9.25..2017 Once this is performed, patients will return for their standard pre-operative clinic visit. Patients will then be randomized once they check-in to the waiting room.

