Randomization: Randomization assignment will be generated by a computer based randomization table and assigned by a research coordinator not otherwise involved in the study. Assignments will be kept in sealed opaque envelopes numbered sequentially. As an adjunct to standard pre-operative counseling, the physician will call the research coordinator and the next envelope in the sequence will be opened randomizing the patient to the patient-centered or physician centered video

Once randomized, patients will view the video they are assigned to in the waiting room utilizing video viewing devices with headphones. Once the video is complete, patients will receive standard pre-operative counseling for the midurethral sling procedure by their provider. The pre-operative counseling will be scripted. They will then complete the PPQ, preparedness scale, SDS-PFD, DCS.

At the 6 week post-operative visit, they will fill out the questionnaires: SDS-PFD, DRS-PFD, and STAI: Y6, UDI-6, PGI-I will be completed (Table 1). The physician will also complete an adverse events form at that time.

	Baseline Clinic Visit	Immediately after consents and video	6 weeks postoperatively
PPQ		Χ	X
Preparedness Scale		X	
DCS		X	
DRS-PFD			X
SDS-PFD		X	X
UDI-6	X		X
Demographics	X		

Table 1: Outcomes collected at various time points

The primary outcome is preparedness for surgery with an adjunct patient-centered versus a physician-centered video at their pre-operative visit. After they watch the video in the waiting room, all patients will receive standard pre-operative counseling for the midurethral sling procedure by their provider. They will then fill out the preparedness questionnaires. Our secondary outcome is satisfaction, which will also be evaluated using the SDS-PFD at her pre-operative visit after consents and the video as well as their 6 week visit.

The midurethral sling will be performed by surgeons in the standard fashion.

Outcome Measures:

- 1. Patient Preparedness Questionnaire (PPQ): Assess the level of pre-operative preparedness according to each preparedness question. Measured by question 11 on the Patient Preparedness Questionnaire (PPQ): "Overall, I feel prepared for my upcoming surgery." The 11-question PPQ contains questions on both knowledge and preparedness for the planned surgical procedure. The PPQ has demonstrated construct validity properties in previous studies.

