Randomization assignment will be generated by a computer based randomization table and assigned by a research coordinator not otherwise involved in the study. Assignments will be kept in sealed opaque envelopes numbered sequentially, and on the day of the patient's pre-operative visit, the surgeon will call a research coordinator who will open the next envelope in the sequence. This de-identified study subject number will then be assigned to the patient. All data collection sheets and questionnaires will contain the subject number and day of the hospital or clinic visit. No other patient identifiers will be collected. PHI including patient name, date of birth,

Page 13 of 23

phone number, medical record number will need to be collected to track for appointments.

The data collection, HIPAA and consent forms will be maintained in a locked file cabinet in the OBGYN administrative area. A separate folder will be designated for each participant. The offices have the additional security of being badge-access only for OBGYN department employees. A key matching study number to subject's name will be secured in a locked file cabinet in the OBGYN research administrative area.

The only PHI collected will be patient name, date of birth, medical record number and telephone number for site use only and to ensure patient follow up. This will not be entered into the database, but it will be kept with the other identifying information.

The data does not include sensitive information or information requiring additional protection.

All data will be kept in a locked file cabinet in the research administrative area. In order to further ensure patient confidentiality, the identifying information will be kept separately from the numbered study files in a locked cabinet.

Electronic data entry will be performed in the OBGYN administrative offices at UNM A REDCAP database will be created through UNM to collect, store and manage the data. REDCAP databases are reposed securely. The REDCAP database is only accessible using a individual unique login and password and access is only provided to co-investigators. Access is restricted to co-investigators and will be protected using the unique REDCAP login and password provided to each co-investigator.

A Certificate of Confidentiality will not be used to protect data from forced release. No data will be transported to outside locations. There will be no audio or video recordings or photographs taken.

16.Data and Specimen Banking

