report any illness or injury they believe to be related to the study to the investigator or research staff. Participants will be given telephone contact information for the urogynecology office for the purpose of asking any questions or stating any concerns about the study or treatment as a research subject. They may also be directed toward the HRPO. This language will be stated in the written consent document, and reviewed during the informed consent process. Again, the patient undergoes an informed consent process for the surgical procedure regardless of enrollment in the study; hence, there is no additional risk to participate in this study.

24. Consent Process

Patients will be approached about the research study at the urogynecology clinics during a discussion for the management of stress urinary incontinence. Each patient undergoes counseling in a private room with a closed door to ensure privacy. All of the physicians in the urogynecology division will obtain consent, given that they are the ones providing the surgical care. They routinely perform this procedure and thus are highly qualified to counsel patient regarding the risks, benefits, and alternatives to the procedure. Those recruited will have already decided to undergo a corrective mid urethral sling procedure. Study consent will be obtained by one of the research team members. Additionally, care will not be withheld if they decide not to participate.

The patients who would like to participate in the study will be consented during their pre-operative visit in the urogynecology clinic. There is a variable amount of time between the decision to undergo surgery and their next visit for their pre-operative assessment, but it ranges from a few days to months. Hence, the patient will be counseled on the study upon the decision to undergo surgery, during their pre-operative visit, and again during the day of surgery. They will have these multiple opportunities to ask any questions that they may have, and they will also be provided with the clinic's contact information to get in touch with research investigators to address any additional questions or concerns.

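### The physician's call opens the envelope before counseling, and nothing keeps the arm from the counseling provider before the patient rates her preparedness

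*Combined protocol and SAP*

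**What the plan says.** Section 11 (Study Procedures) sets the order of events at the pre-operative visit:

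- Timing of randomization: "Patients will then be randomized once they check-in to the waiting room".
- Trigger, under Randomization in the same section: "the physician will call the research coordinator and the next envelope in the sequence will be opened". Section 15 (Data Management/Confidentiality) repeats the step for the day of that visit: "the surgeon will call a research coordinator who will open the next envelope in the sequence".
- Next steps: the patient watches the assigned video in the waiting room with headphones. Then, "Once the video is complete, patients will receive standard pre-operative counseling for the midurethral sling procedure by their provider".
- Control on the counseling, one sentence: "The pre-operative counseling will be scripted".
- Last step: she completes the PPQ, Preparedness Scale, SDS-PFD and DCS. The primary measure is PPQ question 11, her own overall rating of how prepared she feels.

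The envelopes are sealed, opaque and sequentially numbered, and the assigning coordinator has no other role in the study. Section 26.1 says patients will know their arm. No section says whether the counseling provider will.

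On who the physicians are, Section 24 says: "All of the physicians in the urogynecology division will obtain consent, given that they are the ones providing the surgical care". Section 11 says of the physician-centered video: "Physicians from the urogynecology division will be videotaped explaining these risks".

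**The concern.** The assignment is obtained on a physician's call before a conversation whose purpose is to prepare the patient, and the primary outcome is her self-rating straight after it. A provider who knows the arm could, without intending to, make up for a video thought weaker or reinforce one thought stronger. Some of the division's physicians also appear in one of the two videos, so they may not be indifferent between the arms.

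This is performance bias after assignment. It could push the between-arm difference either way, and the analysis in Section 12 has no means of detecting or correcting it. Patients cannot be masked to the video they watch, but the provider can be, at least in part. The open-label nature of the trial therefore does not settle the matter.

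**Working it through.** **Step 1. Is the caller the counselor?** Section 11 has the physician call, as an adjunct to standard pre-operative counseling, and has the patient's provider counsel. Section 15 has the surgeon call. Section 24 says the division's physicians obtain consent because they provide the surgical care, and describes them as qualified to counsel on the procedure. Together these make it likely that one person does both. No sentence says so.

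**Step 2. Does the caller learn the arm?** In both sections the coordinator opens the envelope. Section 15 mentions a study subject number assigned to the patient as a result. Neither section says the arm is read out to the caller, and neither says it is withheld. Somebody at the clinic must be told which video to play, and no one other than the caller is named.

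**Step 3. Does the order of events allow bias?** Call, video, counseling, questionnaires. Knowledge gained on the call would precede counseling, and counseling precedes the primary rating. The script limits content and, to a degree, length. It cannot fully fix tone or answers to questions, and no check on adherence is described.

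**Step 4. The plan's own figure.** Inputs from Sections 5 and 12: 40% versus 78% completely prepared, 80% power, alpha 0.05 (two-sided assumed, since sidedness is not stated), chi-squared test.

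- Pooled-variance formula, mean proportion (0.40 + 0.78)/2 = 0.59: n = [1.960·√(2·0.59·0.41) + 0.842·√(0.40·0.60 + 0.78·0.22)]² / 0.38² = 25.1, so 26 per group.
- Exact power of the uncorrected chi-squared test at the stated 24 per group: 80.1%.
- Allowance for 20% loss: 24/0.80 = 30 per group, 60 in total.

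The stated sample size reproduces within two patients per group, and this point does not change it.

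**Step 5. What a bias would do, by assumption.** The documents give no estimate of how far arm-aware counseling could move the rating. The shifts below are assumptions chosen to show a range. For each pair of true rates, the rejection probability is the sum of Bin(a; 30, p1)·Bin(b; 30, p2) over all outcomes (a, b) where the uncorrected Pearson test gives p ≤ 0.05 two-sided.

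No video effect, one arm shifted upward by counseling:

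| Assumed shift | Rates compared | Chance of a significant result |
|---|---|---|
| 0 points | 40% vs 40% | 4.9% |
| 5 points | 40% vs 45% | 6.8% |
| 10 points | 40% vs 50% | 12.3% |
| 15 points | 40% vs 55% | 21.8% |

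Video effect as planned, providers compensating in the physician-video arm:

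| Assumed shift | Rates compared | Power |
|---|---|---|
| 0 points | 40% vs 78% | 86.8% |
| 5 points | 45% vs 78% | 76.1% |
| 10 points | 50% vs 78% | 62.3% |

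At 24 evaluable per group, the 10-point compensating shift lowers power from 80.1% to 54.4%.

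**The case against.** The strongest reply has four parts.

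- **The text does not describe an unmasking.** A reader might infer that the surgeon who counsels is told the arm on the telephone. The documents do not support that as fact: caller and counselor are never expressly identified as one person, and nothing says the arm is disclosed to the caller. This stands, and it confines the point to a missing safeguard.
- **The main control is already there.** Counseling is scripted in both arms and the video is watched on headphones. This stands in part. The script narrows the room for bias, but tone and answers to questions remain open and adherence is not checked.
- **The magnitudes have no anchor.** This stands in full. Nothing in the documents supports a shift of 5, 10 or 15 points under scripted counseling. At 5 points the false-positive rate moves only from 4.9% to 6.8%. The tables show what a bias of a given size would do, not that one is likely.
- **Masking the provider leaves the larger problem.** Patients know their video, rate the outcome themselves and may mention the video during counseling. This also stands, but it does not argue for leaving an avoidable leak open.

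A reader might also take this for a failure of allocation concealment. It is not: sealed, opaque, sequential envelopes held by an independent coordinator protect the assignment until it is made.

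**Conclusion.** The point holds as a preventable weakness. The plan lets the probable counseling provider make the call that opens the envelope, and does not keep the arm from that person before the self-rated primary outcome is complete. Scripting reduces the risk without removing it.

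The size and direction of any bias are unknown. The figures in the working rest on assumed shifts, 30 analyzed per arm, a 40% base rate and the uncorrected chi-squared test. They do not show that the result would be biased, nor that the video effect would be impossible to separate from counseling. What justifies the change is that the remedy is cheap and the bias, if it occurred, could not be corrected afterwards.

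**What to change.** Amend the randomization text in Sections 11 and 15 alike:

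1. Existing clinic or research staff who do not counsel the patient call the coordinator when she checks in, and start the assigned video. This agrees with the check-in timing already in Section 11.
2. The coordinator keeps only the envelope role. Having the coordinator play the video as well would fit poorly with that person's independence, and with someone reached by telephone from several clinics.
3. State that the counseling provider is not told the arm until the PPQ, Preparedness Scale, SDS-PFD and DCS are complete, and record any unmasking before then.
4. Patients may be asked not to name the video they saw, but must remain free to ask any question.

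The cost is protocol wording and a change in who places the call. Each clinic needs a non-counseling staff member available at check-in. The documents describe research staff but do not confirm cover at every site, so this should be checked. No visits or patients are added and the sample size is unchanged. Masking will be partial, since patients may reveal their video, and bias from the patient's own awareness of her arm remains.

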Power Analysis: We will compare the percent of patients that feel completely prepared (strongly agree on the Patient Preparedness Questionnaire, a 1-6 Likert scale) between the two intervention groups, those randomized to a Physician-centered vs Patient-centered video. Firoozi et al. found 30% were "completely prepared" in the standard office counseling group. However, we expect a "floor effect" where a higher percentage of completely prepared at 40%. As there is high satisfaction in this population that will be undergoing mid-urethral sling surgery. A sample size of 24 patients per group would be adequate to detect a difference of 40% (Physician-centered video) versus 78% (Patient-centered video) in those being "completely prepared" with 80% power and an alpha of 0.05. This is a feasible power analysis since Firoozi et al found an improvement to 79% using the shared appointments. Therefore our recruitment goal will be to increase randomization to a total of 60 subjects, 30 patients per group, which will also allow for a 20% loss to follow up.

6. Study Timelines

Based on the current surgical volume in the UNM division of urogynecology, it will take 12 months to recruit the 43 patients; it would take 18 months to recruit~ 60 patients. Then, for data analysis and composition of the manuscript, we estimate that this will take 6 months.

Page 7 of 23

Timeline	Feb. 2017- May 2017	June 2017- Dec. 2018	Jan 2019-March 2019	April 2019- June 2019
Video Development	\longleftrightarrow			
Subject recruitment, surgery, through 6 week follow up				
Data analysis		•	*	
Manuscript preparation				\longleftrightarrow

7. Study Endpoints

First, the physician-centered and patient-centered video will be created. Once developed, the **primary endpoint** of our study is to determine if there is a difference in patient preparedness and satisfaction in those women undergoing a MUS procedure who have watched a patient-centered versus a physician-centered video watched at their pre-operative visit. Our **secondary endpoints** include differences in preparedness, satisfaction and decisional conflict scores. Our **exploratory endpoint** is to investigate differences in anxiety 6 weeks after corrective MUS surgery in those who undergo a pre-operative patient-centered video compared to a physician-centered video.

Given that a MUS surgery is routinely performed currently, we do not have any **safety endpoints**.

8. Research Setting

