- 2. Decision Regret Scale- Pelvic Floor Disorders (DRS-PFD): Validated pelvic floor disorder questionnaire. It is designed to measure regret after health care decisions. This is a modified scale that is specific for women making decisions regarding surgical therapy for PFDs.
- 3. Satisfaction with Decision Scale-Pelvic Floor Disorders (SDS-PFD): Validated pelvic floor disorder questionnaire. This is a modified 6-item questionnaire with a 5-point response scale to measure patient satisfaction.
- 4. Urinary Distress Inventory 6 (UDI-6): This is a validated shortened version of the UDI questionnaire to assess symptom distress and the impact of daily life of urinary incontinence. It is a 6-question instrument that correlates well with the longer version.
- 8. Decisional Conflict Scale (DCS): A questionnaire that has been adapted and validated for Pelvic Floor Disorders. This contains 16 questions with a five-point response scale. The mean score is multiplied by 25 to report it on a 100-point scale with 0 correlating to no decisional conflict and 100 with extremely high decisional conflict.
- 9. Preparedness Scale: Measures extent to which a subject that she was prepared pre-operatively for their surgery on a 0 to 10 scale.

12.Data Analysis

Data Analysis: The main comparison is of the overall preparedness questionnaire item on the patient preparedness questionnaire (PPQ) between the two intervention groups of patients (physician- vs. patient- centered videos) using the Chi-Squared test for categorical data, since the questionnaire item responses are on a Likert scale. Other analyses will be done by a 2-way ANOVA with both intervention groups and the item members considered to be 2 grouping factors.

Power Analysis: We will compare the percent of patients that feel completely prepared (strongly agree on the Patient Preparedness Questionnaire, a 1-6 Likert scale) between the two intervention groups, those randomized to a Physician-centered vs Patient-centered video. Firoozi et al. found 30% were "completely prepared" in the standard office counseling group.⁶ However, we expect a "floor effect" where a higher percentage of completely prepared at 40%. As there is high satisfaction in this population that will be undergoing mid-urethral sling surgery. A sample size of 24 patients per group would be

Page 12 of 23

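### The two-way ANOVA named in Section 12 for all non-primary analyses has no term for the woman, so its test of the video effect on multi-item scales rejects far too often

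*Combined protocol and SAP*

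**What the plan says.** Section 12 (Data Analysis) gives two rules. The overall PPQ item is compared between arms by a chi-squared test. For the rest there is one sentence: "Other analyses will be done by a 2-way ANOVA with both intervention groups and the item members considered to be 2 grouping factors". No subject factor, random effect, repeated-measures structure or clustered error is mentioned there or elsewhere.

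Section 11 describes the instruments this would reach:

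- PPQ: "The 11-question PPQ contains questions on both knowledge and preparedness for the planned surgical procedure". The aim is also put at item level: "Assess the level of pre-operative preparedness according to each preparedness question".
- SDS-PFD: "This is a modified 6-item questionnaire with a 5-point response scale to measure patient satisfaction".
- UDI-6: "It is a 6-question instrument that correlates well with the longer version".
- DCS: 16 questions, reduced to one 0–100 score per woman.
- STAI: the 6-item form, named in Aim #4.
- DRS-PFD: number of items not given.
- Preparedness Scale: a single 0–10 rating.

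On the standing of these outcomes, Section 7 words the primary one as follows: "of our study is to determine if there is a difference in patient preparedness and satisfaction in those women undergoing a MUS procedure". Its list of secondary ones is said to "include differences in preparedness, satisfaction and decisional conflict scores". Section 11 places satisfaction differently: "Our secondary outcome is satisfaction, which will also be evaluated using the SDS-PFD at her pre-operative visit after consents and the video".

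**The concern.** The unit of randomisation is the woman. When a multi-item scale is laid out as one row per answer and analysed with arm and item as the only factors, the arm effect is tested against the spread of single answers. A woman who is generally satisfied tends to score high on every item, so her six answers carry much less than six independent pieces of information about her arm. The ANOVA treats them as six.

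Satisfaction has most at stake. It is part of the central hypothesis, sits in the primary endpoint in Section 7, and is measured by a 6-item scale at two time points. The trial could report that the patient-centered video improves satisfaction, or the PPQ items as a group, when it does nothing. The sentence also sits badly with Section 7, which speaks of differences in scores, and with the DCS description, which yields one score per woman. An arm-by-item ANOVA does not analyse one score per woman.

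**Working it through.** **Inputs from the document.** Evaluable women per arm n = 24, randomised 30 per arm, alpha 0.05 (Sections 5 and 12). Items per scale k: 6 (SDS-PFD, UDI-6, STAI), 11 (PPQ), 16 (DCS).

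**Assumptions.** The inter-item correlation ρ is not in the document. I take 0.3 to 0.5 as the working range and show 0.1 to 0.6. Alpha is stated only for the primary comparison; I assume a two-sided 0.05 for the others.

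**The plan's own figure.** The document gives no number for the ANOVA. Its sample size for 40% versus 78% at 80% power is 24 per group. Standard formulas give 22.4 (unpooled), 24.8 (arcsine) and 26 (pooled), and power at 24 per group is 78.1%. Allowing for 20% loss, 24/0.8 = 30. So 24 per group is a fair basis for what follows.

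**Step 1: degrees of freedom.** With 24 per arm and the interaction in the model:

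- 6 items: 2 × 24 × 6 = 288 rows, error df 2 × 6 × 23 = 276.
- 11 items: 2 × 24 × 11 = 528 rows, error df 2 × 11 × 23 = 506.
- Correct error df for the arm effect in both cases: 48 − 2 = 46 (58 with 30 per arm).

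**Step 2: variance.** With equal correlation ρ between items, the variance of the arm difference is larger than the ANOVA assumes by DE = 1 + (k − 1)ρ. The ANOVA standard error is therefore 1/√DE of its correct size. For 6 items this is 0.63 (ρ = 0.3) to 0.53 (ρ = 0.5). For 11 items it is 0.50 to 0.41.

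**Step 3: true false-positive rate.** Rate = 2 × [1 − Φ(1.96/√DE)]. For 6 items at ρ = 0.3: DE = 2.5, 1.96/1.581 = 1.24, rate 21.5%. For 11 items at ρ = 0.5: DE = 6.0, 1.96/2.449 = 0.80, rate 42.4%. The simulated rates in the table come from null data with a random woman effect, 24 per arm and 10,000 datasets per setting.

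| Items | ρ | DE | Formula | Simulated |
|---|---|---|---|---|
| 6 | 0.1 | 1.5 | 11.0% | 10.8% |
| 6 | 0.3 | 2.5 | 21.5% | 21.3% |
| 6 | 0.5 | 3.5 | 29.5% | 29.9% |
| 6 | 0.6 | 4.0 | 32.7% | 32.8% |
| 11 | 0.1 | 2.0 | 16.6% | 17.1% |
| 11 | 0.3 | 4.0 | 32.7% | 33.1% |
| 11 | 0.5 | 6.0 | 42.4% | 42.3% |
| 11 | 0.6 | 7.0 | 45.9% | 45.6% |

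For 16 items the formula gives 40.3% (ρ = 0.3) and 50.1% (ρ = 0.5). That applies only if the DCS is analysed by item, against its own definition.

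**Step 4: robustness.** With 30 per arm, the simulated rates at ρ = 0.3 and 0.5 are 21.2% and 29.7% (6 items) and 32.4% and 43.1% (11 items). Dropping the interaction changes the 24-per-arm rates in the table by at most 0.4 points. With skewed Likert answers at 24 per arm, the rates are 19.5% and 27.3% (6 items) and 29.7% and 40.5% (11 items).

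**Step 5: what a reported p-value would mean.** A p of 0.05 from the stated ANOVA on 6 items is t = 1.969 on 276 df. At ρ = 0.3 the correct statistic is 1.969/1.581 = 1.245 on 46 df, p about 0.22; at ρ = 0.5, p is about 0.30. For 11 items the correct p is about 0.33 to 0.43.

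**Step 6: check of the remedy.** A t-test on one mean per woman rejected in 4.7 to 5.2% of the same null datasets. Testing arm against between-woman variation, F(1,46), gave the same p-value as that t-test in every balanced dataset.

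**What is not inflated.** The primary chi-squared test uses one answer per woman, and the Preparedness Scale has no item factor. The arm-by-item interaction errs the other way, rejecting in 0 to 3%.

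**The case against.** The strongest reply is that the sentence is shorthand. A split-plot ANOVA, with arm between women and item within women, also has two named factors and would use women as the error term for arm. That may have been the intention. But nothing in the document says so, calling both terms grouping factors points the other way, and an analyst following the text would leave the woman out. If a repeated-measures analysis was meant, the correction only writes it down.

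A second reply concerns scope. The sentence follows directly on the PPQ item, and other outcomes are described elsewhere as scores, so it may have been meant for the PPQ items alone. That is plausible, and a scale analysed as one score per woman has no inflation. The wording is not so limited, however. On the narrow reading the PPQ items are still affected: 31 to 40% at ρ = 0.3 to 0.5 if the primary item is set aside and ten remain (DE 3.7 and 5.5). The other scales would then have no stated analysis.

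Third, the size depends on a correlation the document does not give, and the PPQ mixes knowledge with preparedness questions, so a single common value is a simplification. This stands. The direction does not depend on it: any positive correlation makes the arm test too liberal.

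**Conclusion.** The concern holds. As written, Section 12 prescribes an analysis with the wrong error term for the arm effect on every multi-item scale analysed by item. The true false-positive rate at a nominal two-sided 5% is about 21 to 30% for 6 items and 33 to 42% for 11, assuming an inter-item correlation of 0.3 to 0.5. Over 0.1 to 0.6 the ranges are 11 to 33% and 17 to 46%. No figure is claimed for the DRS-PFD, whose item count is not given. The damage is confined to the secondary and exploratory comparisons, and to satisfaction where Section 7 counts it as primary; the main PPQ comparison and the sample size stand. The plan should be corrected before these outcomes are analysed.

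**What to change.** Replace the ANOVA sentence in Section 12 with text to this effect:

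*Each multi-item scale other than the PPQ is reduced to one score per woman at each time point, and arms are compared on that score by a two-sample t-test: DCS and SDS-PFD after the video and counseling; SDS-PFD, DRS-PFD, UDI-6 and STAI at 6 weeks. The Preparedness Scale rating is compared in the same way. Item-level analyses, including the PPQ items, are done separately at each time point with a mixed model that has fixed effects for arm and item and a random intercept for woman, so that arm is tested against between-woman variation.*

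Four additions complete it:

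- State the scoring rule for every scale. Only the DCS rule is written out, and no PPQ total is defined, which is why the PPQ stays at item level.
- Name a small-sample degrees-of-freedom method for the mixed model, since there are only about 48 to 60 women.
- Give the PGI-I, also collected at 6 weeks, a stated analysis.
- Say whether satisfaction is a primary or a secondary outcome, since Sections 7 and 11 differ.

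Adjusting the 6-week STAI and UDI-6 comparisons for the baseline scores already collected would be a sensible option for precision, but it is a separate matter.

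The cost is a few sentences, with no new data and no more patients. Secondary p-values will be larger, and fewer secondary results will reach 0.05.
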